4.1 OVERALL DESIGN

In aim 1, with relevant stakeholders in adolescent HIV, we will collaboratively develop the DiSC intervention, then adapt and pilot test the intervention.

In aim 2, we will conduct a cluster randomized trial (cRCT) in up to 24 sites in western Kenya (12 randomized to intervention and 12 to control) (Figure 1).

Figure 1: Study design, main activities, and outcomes

Adapted from NIH Behavioral and Social Intervention Clinical Trial Protocol Template v3.0 - 20180827

Study hypothesis

- Primary and secondary outcomes: We hypothesize that the DiSC intervention will result in better retention, adherence and viral suppression among adolescents in the intervention sites compare to those in control sites. Hypothesized psychosocial outcomes will include better psychosocial and family support, mental health, family support and adolescent self-efficacy.
- We hypothesize the DiSC intervention will be associated with improved clinic efficiency (client wait time), and will be cost effective.
- The DiSC Intervention will be feasible, acceptable to HCW and adolescents but will require clinic specific intervention adaptations.

Randomization

Up to 24 clinics will be randomized in a 1:1 ratio using computer generated random numbers to either intervention or control, using restricted randomization to balance by county, aiming to balance the numbers of clinics from each county between arms. Timing of randomization will be prior to study start. Randomization will be done at the University of Washington by a biostatistician not involved in study procedures. A list of clinics with their allocation arms will be sent to the study team. We will perform individual substitutions of sites on a case by case basis, as needed (e.g. if the site no longer meets an eligibility criterion). The intervention is administered at the clinic-level; it is not possible to blind participating clinics or study team members.

Study intervention

The DiSC intervention is comprised of a system to assign adolescents to care based on their health needs and the different levels of care for each assignment group. Control sites will continue with standard of care approaches for adolescent clinic visits (usually 1-3 monthly visits) regardless of health care needs and additional support as needed.

Analysis

Adapted from NIH Behavioral and Social Intervention Clinical Trial Protocol Template v3.0 - 20180827

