9.2 SAMPLE SIZE DETERMINATION

Sample Size and Power for primary outcome

In our sample of HIV care facilities with >1,000 clients enrolled overall, we anticipate at least 10% will be eligible adolescents and young adults or about 100-200 AYA per clinic on average. Based on our UG3 data, we assume that 75% will be in care (not LTFU) and viral suppression of 64% (85% suppressed x 75% actively in care). Given a minimum of 20 facilities in the trial (minimum 10 per arm), we estimated the minimum average number of AYA per facility to detect a 15-20% change in retention using EMR data. We assumed 80% power, an $\alpha=0.05$ and coefficient of

Adapted from NIH Behavioral and Social Intervention Clinical Trial Protocol Template v3.0 - 20180827

variation of 0.15. In table 3a below, we can detect a 17% percentage point different (75% to 93%) with an average of 100 AYA per facility and 20 facilities. The same estimates hold for as few as 50 AYA per arm and up to 170 per arm. Detecting less than a 17% percentage point difference would require more facilities per arm or at least 180 AYA per facility.

Secondary outcomes and assumptions:

Viral suppression: An average of 50 AYA VL records per facility and a minimum of 10 facilities per arm would be sufficient to detect a change from 64% to 81%, assuming 80% power, an $\alpha=0.05$ and coefficient of variation of 0.15.

Cohort analyses: Based on UG3 enrollment data in the AYA cohort, we assume that about 50% of the total AYA clinic population to enroll in the cohort and set 50 as the average enrollment target per facility. Separate power and sample size calculations will be performed based on the specific exposure and outcome. When the intervention is the exposure, we will assume to have adequate power to detect at least a 17% percentage point difference in proximate outcomes (e.g. implementation and client outcomes)

Table 3a: Minimum Sample of AYA per Facility for the Primary ITT Analysis of Retention

	Retention % in the intervention arm	n=100 AYA per facility	Facilities per arm	n=50 AYA per facility	Facilities per arm
75%	90%	100	13	50	14
75%	92%	100	11	50	12
75%	93%	100	10	50	10

Table 3b: Summary of sample size estimates by outcome

Outcome	Source	Sample size	
		Intervention	Control
Retention	EMR data	3000	3000
Unsuppressed VL	EMR data	3000	3000
Mediators and secondary outcomes	Adolescent surveys	1500	1500
	Caregiver surveys	450	450
Implementation outcomes	HCW surveys	120	120
	HCW implementation logs	12	0

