1.2. DiSC Cluster RCT Objectives

Primary: To compare retention during 12-month follow-up among ALHIV in 12 HIV clinics receiving DiSC intervention to retention among ALHIV in 12 similar control clinics receiving standard of care. Participating clinics will be high-volume HIV clinics in Homabay, Kisumu and Migori counties, all in Western Kenya.

Secondary: To evaluate the effect of the DiSC intervention on HIV cascade outcomes (viral non-suppression, receiving differentiated care, adherence).

Section 2. Study outcomes

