2.2. Sample size considerations

2.2.1. Sample size and power for primary outcome

In our sample of HIV care facilities with >1,000 clients enrolled overall, we anticipate at least 10% will be eligible adolescents and young adults (AYA), with about 100-200 AYA per clinic on average. Based on our UG3 data, we assume that 75% will be in care (not LTFU) by the end of 12-month follow-up period. Given a minimum of 24 facilities in the trial (minimum 12 per arm), we estimated the minimum average number of AYA per facility to detect a 14-18% point change in retention using EMR data. Assuming 12 facilities per arm, 80% power, $\alpha=0.05$ and coefficient of variation of 0.10 (Table 2), we can detect a 14%-point difference (75% to 89%) with at least 150 AYA per facility, and a 15%-point difference (75% to 90%) with at least 50 AYA per facility. Assuming coefficient of variation of 0.15, we can detect a 17%-point difference (75% to 92%) with at least 50 AYA per facility (Table 2). Detecting a less than 14%-point difference or if assuming a larger correlation coefficient of individuals within a facility would require more participants per facility or more facilities per arm.

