2.2.2. Secondary outcomes and assumptions

Viral suppression: An average of 50 AYA VL records per facility and a minimum of 12 facilities per arm would be sufficient to detect a change from 64% to 82%, assuming 80% power, an $\alpha=0.05$ and coefficient of variation of 0.10 (Table 2).

Table 1. Sample size calculation of number of facilities per arm for the ITT analysis of retention and viral suppression

AYA per facility	ICC	Estimated proportion in study arm									
		Control	Intervention								
		75%	85%	86%	87%	88%	89%	90%	91%	92%	93%
200	0.10		26	21	18	15	12	11	9	8	7
150			27	22	18	15	12	11	9	8	7
100			27	22	18	15	13	11	9	8	7
50			30	24	20	17	14	12	10	9	8
	0.15	75%	85%	86%	87%	88%	89%	90%	91%	92%	93%
200			39	31	26	21	18	15	13	11	10
150			39	32	26	22	18	16	13	12	10
100			40	32	26	22	19	16	14	12	10
50			42	34	28	23	20	17	14	12	11
		64%	80%	81%	82%	83%	84%	85%	86%	87%	88%
200	0.10		13	11	10	9	8	7	6	6	5
150			13	12	10	9	8	7	7	6	5
100			13	12	10	9	8	7	7	6	5
50			15	13	11	10	9	8	7	7	6
	0.15	64%	80%	81%	82%	83%	84%	85%	86%	87%	88%
200			19	17	15	13	12	10	9	8	8
150			19	17	15	13	12	10	9	8	8
100			19	17	15	13	12	11	10	9	8
50			20	18	16	14	12	11	10	9	8

ICC: intraclass correlation coefficient; sample size estimated by assuming study power of 80%, significance level of 0.05 and coefficient of variation of 0.10

Section 3. Study Data Analysis

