3.4. Analysis of retention

Retention will be evaluated using an indicator of missed visits. A missed visit will be defined as a participant not seen within 30 days of a scheduled visit during follow-up since the first stepped care visit to 12 months. Each scheduled visit will be classified as missed versus not missed and analysis will use repeated measures per participant. The proportion of missed visits will be compared between study arms using mixed-effects Poisson regression with random effects for facility and participant and robust standard errors.

Sub-group analyses for retention will be performed by gender and age-group. Facility factors, including concurrent adolescent-friendly services and high/low performance will be evaluated as modifiers of intervention effectiveness.

Table 4. Analysis of missed visits

	Overall	Control	Intervention	Intervention vs. control
Missed visits per participant				^a RR (95% CI)
Median (IQR)				
Number of scheduled visits				
Number of missed visits (%)				
Missed visits over all participants				
Count (proportion)				
Number of scheduled visits				
Number of missed visits (%)				
Number of AYA ever missed a visit (%)				

^a Estimated by mixed-effects Poisson regression with random effects for facility and participant and robust standard errors

*Excluding TCA that had miss/no-miss status censored or missing

*Models adjusted for any factors differing between arm with statistical significance at enrollment

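### The SAP names no small-sample method for its mixed-effects Poisson models on 24 clinics; with ordinary z inference the nominal 5% test would run at about 6-7.5% if county explains little of the between-clinic variance

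*SAP*

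**What the plan says.** - **Units.** SAP 1.2 compares "12 HIV clinics receiving DiSC intervention to retention among ALHIV in 12 similar control clinics". SAP 2.2.1 plans on "Given a minimum of 24 facilities in the trial (minimum 12 per arm". The protocol is looser: section 4.1 says "Up to 24 clinics will be randomized in a 1:1 ratio", with allocation restricted to balance county, and section 9.2 plans on "Given a minimum of 20 facilities in the trial (minimum 10 per arm".
- **Primary model.** SAP 3.4 analyses each scheduled visit as missed or not, using "mixed-effects Poisson regression with random effects for facility and participant and robust standard errors", and Table 4 reports a rate ratio with a 95% interval.
- **Secondary models.** SAP 3.5.2 to 3.5.4 use the same model for viral non-suppression, long inter-visit interval, fast-track visits and adherence. SAP 3.5.1 uses Poisson regression with robust errors for the loss-to-follow-up proportion and Cox regression for time to loss. It mentions clinics for neither.
- **Covariates.** The footnotes to Tables 4 and 5 add only factors found to differ significantly between arms at enrolment. County is not named.
- **Not stated.** Neither document gives a reference distribution for the arm effect, its degrees of freedom, a small-sample variance correction, a permutation test or a clinic-level analysis.

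**The concern.** Because clinics are randomised, the information about the arm effect is limited by the number of clinics. Several thousand participants with repeated visits add precision within clinics but no degrees of freedom between them. Two things go wrong when about 24 units are treated as a large sample. The normal critical value is too small for a variance estimated on about 22 degrees of freedom, and an uncorrected sandwich variance is biased downward. Both push the same way: too many false positives and intervals that are too short.

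At stake is the confirmatory test of the single primary outcome. The planned sample size leaves no slack, so the choice of reference distribution could decide a borderline result. That choice should not be open once the data have been seen.

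**Working it through.** **Inputs.** 12 clinics per arm (SAP 2.2.1), with 10 per arm as the protocol's minimum (section 9.2); alpha 0.05 and 80% power; "we can detect a 14%-point difference (75% to 89%) with at least 150 AYA per facility" with a between-clinic parameter of 0.10. The SAP calls this parameter a coefficient of variation in the text and an ICC in the table. I treat it as an ICC because that reproduces the table. The type I error results in step 2 do not depend on it.

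**1. Reproducing the plan's figure.** Clinics per arm = (1.960 + 0.842)² × [p1(1−p1) + p2(1−p2)] × [1 + (m−1)ICC] / (m d²).

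For 75% v 89% and m = 150: 7.849 × 0.2854 × 15.9 / (150 × 0.0196) = 12.11, against 12 stated. The same formula matched 106 of the 108 cells checked exactly after rounding up, and the other two differed by 1. So the SAP's planning uses normal quantiles with no allowance for few clinics.

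**2. Size of a nominal 5% test judged against 1.96.** The clinic-level contrast follows t with G − 2 degrees of freedom. The uncorrected sandwich variance is too small by (n−1)/n per arm, here 11/12.

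| Variance | Formula for 24 clinics | 24 clinics | 20 clinics |
|---|---|---|---|
| Unbiased | 2P(t22 > 1.96) | 6.3% | 6.6% |
| Sandwich with G/(G−1) | 2P(t22 > 1.96√(11/12 × 24/23)) | 6.8% | 7.3% |
| Uncorrected sandwich | 2P(t22 > 1.96√(11/12)) | 7.4% | 7.9% |

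Width of the correct interval relative to the z interval (log scale, 24 clinics): 2.074/1.960 = 1.058; with the sandwich correction 1.058 × √(12/11) = 1.105; against a sandwich already scaled by G/(G−1), 1.082.

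**3. Simulation under no effect.** Event rates, visits per participant and between-clinic spread are not in the documents and were assumed.
- Clinic random-intercept Poisson model, missed-visit rate 10% or 25%, log-scale clinic SD 0.3 or 0.5, about 150 participants with 5 visits each, 24 clinics. The size was 7.4-7.9% with an uncorrected sandwich and z, 6.8-7.5% with G/(G−1), and 7.4-7.8% with model-based standard errors and z. A t reference plus a 12/11 variance factor gave 4.9-5.6%. Monte Carlo error is 0.5-0.7 points. Participant variation was generated but not fitted as a second random effect.
- One 20-clinic setting gave 6.3% uncorrected and 5.7% with G/(G−1) (Monte Carlo error 0.7 points).
- Beta-binomial data, one outcome per person, ICC 0.10, 100 per clinic, 24 clinics: 7.0% at a 20% event rate and 8.2% at 10%, falling to 5.2% and 6.0% with the correction.

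**4. Effect of the county restriction.** Clinic-level normal outcomes, 300,000 null runs. I assumed three counties of eight clinics, four per arm in each; the documents give neither this split nor county's share of the variance.

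| County share of between-clinic variance | z, unbiased variance | z, uncorrected sandwich | t22, county omitted | t20, county modelled |
|---|---|---|---|---|
| 0% | 6.3% | 7.4% | 5.0% | 5.0% |
| 10% | 5.5% | 6.5% | 4.3% | 5.0% |
| 20% | 4.6% | 5.5% | 3.6% | 5.0% |
| 30% | 3.9% | 4.7% | 3.0% | 4.9% |

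**5. Power at 12 per arm.** For 75% v 89%, m = 150, ICC 0.10, the standardised difference is 0.14/√(0.03025/12) = 2.79. Power is 79.6% with z and 76.0% with t22; 14 clinics per arm would be needed. For 75% v 90%, m = 50, it falls from 81.9% to 78.4%; 13 would be needed.

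**The case against.** **The SAP never says z.** This stands. A reader might infer that the trial's test will run above 5%. The documents do not support that as a fact: they name a model, a variance type and a 95% interval, and leave the reference distribution open. The inflation is conditional on the usual large-sample inference being used. The gap still matters, because nothing in the plan rules that choice out and the plan's own sample-size table is built on normal quantiles.

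**The county restriction works the other way.** This also stands. A factor balanced by design but left out of the model makes the test conservative. At a 20% county share, z with an unbiased variance is already below 5%, and at 30% so is z with the uncorrected sandwich. A plain t22 test would then over-correct. This qualifies the size of the error and changes the remedy, since county has to be in the model.

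**Not every main model is affected in this way.** A reader might extend the 6-8% range to all the SAP's models. It does not fit those in SAP 3.5.1. The Cox model names no robust errors, and the loss-to-follow-up Poisson model names robust errors without saying that they are clustered on clinic. If both are run without clustering, the design effect at ICC 0.10 is 1 + 49 × 0.10 = 5.9 for 50 per clinic and 1 + 149 × 0.10 = 15.9 for 150. The size, 2P(Z > 1.96/√design effect), is then about 42% and 62%. Even ICC 0.01 gives about 11-21%.

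**Robust errors are not the main cause.** A reader might blame the sandwich. Model-based errors with z had nearly the same size in simulation, and the critical value alone accounts for 6.3% of the 7.4%. The cause is few clinics judged against a normal reference.

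**The excess is modest.** True: one to three percentage points at most.

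**Conclusion.** The point holds for the five mixed-effects Poisson analyses: missed visits, viral non-suppression, long interval, fast-track and adherence. On 24 clinics with z inference, the nominal 5% test runs at 6.3-7.4% analytically and at up to about 8% in simulations with assumed event rates. At 6.3-7.4% that is roughly a quarter to a half more false positives than stated. The conclusion rests on two conditions: that z is used, which the SAP neither states nor excludes, and that county explains little of the between-clinic variance. If county explains around 20% or more and is left out, the error largely disappears or reverses, so the stated level is wrong in a direction that cannot be known in advance. The current covariate rule is unlikely to bring county in, because a factor balanced by design should not differ significantly between arms. The matter is worth settling before database lock; it does not undermine the design.

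**What to change.** In SAP 3.4 and 3.5.2 to 3.5.4:

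1. Include county, the randomisation restriction factor, in every model.
2. Test the arm effect, and form its interval, on a t distribution with between-clinic degrees of freedom: 24 − 2 = 22 without county, and 20 with two county terms. Use fewer for any further clinic-level covariate, and recompute if fewer than 24 clinics take part. Use a small-sample-corrected cluster-robust variance and name the correction.
3. Alternatively, specify a clinic-level permutation test over the allocations that the county restriction allows.

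In the county check above, modelling county with t20 held the size at 4.9-5.0% at every county share tried.

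For the two analyses in SAP 3.5.1, state clinic clustering first, for example clinic-clustered errors or a clinic random effect or frailty. A small-sample correction has no meaning there until that is done.

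The cost is SAP wording and an analysis option, with no change to design or data. Intervals become about 6-10% wider than under z. Power for 75% v 89% falls from about 79.6% to 76.0% with t22; county adjustment could recover some of this if county matters. The SAP should report the lower figure instead of implying a full 80%.

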3.5. Analysis of secondary study outcomes

3.5.1. Loss to follow-up:

- Loss to follow-up will be defined as a participant missed a visit and did not return to care within the 12-month study period. The proportion of loss to follow-up during 12-month study interval (window up to 12 months +30 days) will be compared between study arms using Poisson regression with robust errors.
- Time to loss to follow-up will be compared between arms by survival curves, and death or transfers will be censored. The hazard of loss to follow-up will be compared between study arms using Cox proportional hazards regression.

3.5.2. Viral non-suppression:

- Viral non-suppression will be defined as having HIV viral loads (VL) >1,000 copies/mL. Each VL testing result will be classified as VL suppressed vs. unsuppressed. The proportion of viral non-suppression during follow-up will be compared between study arms using mixed-effects Poisson regression with random effects for facility and participant and robust standard errors.

3.5.3. Receiving differentiated care:

- Receiving differentiated care will be defined in two ways. One approach will evaluate the next visit appointment date (scheduled inter-visit interval) – visits scheduled for ≥ 3 months after visit will be considered as differentiated care, in comparison to monthly visits recommended for AYA in current guidelines. The second approach will use the variable ‘fast-track’ at each visit – ‘fast track’ visits are considered as a component of differentiated care. Two analyses will be conducted (one for long scheduled inter-visit interval and one for ‘fast track’), each will be compared between study arms using mixed-effects Poisson regression with random effects for facility and participant and robust standard errors.

3.5.4. Adherence:

- Adherence will be evaluated using the proportion of days of pill dosing over days of inter-visit interval. The level of adherence during the past inter-visit interval will be assessed at each visit. A proportion over 80% as good adherence. The dichotomized adherence will be compared between arms using mixed-effects Poisson regression with random effects for facility and participant and robust standard errors.

Table 5. Analysis of secondary study outcomes

Loss to follow-up				
	Overall	Control	Intervention	Intervention vs. control
	Count (proportion)			^a RR (95% CI) ^b HR (95% CI)
Event Person-year Cumulative incidence Incidence rate (per 100 person-years)				
Viral non-suppression				
	Overall	Control	Intervention	Intervention vs. control
	Count (proportion) / Median (IQR)			^c RR (95% CI)
Per participant Number of viral load assays				
Over all participants Number of viral load assays Number of non-suppression results (%)				
Differentiated care: long-interval visits scheduled				
	Overall	Control	Intervention	Intervention vs. control
	Count (proportion) / Median (IQR)			^c RR (95% CI)
Per participant Number of scheduled visits				
Over all participants Number of scheduled visits Number of long-duration interval (%)				
Differentiated care: fast-track visits				
	Overall	Control	Intervention	Intervention vs. control

DiSC UH3 Statistical Analysis Plan (SAP)

	Count (proportion) / Median (IQR)			°RR (95% CI)
Per participant Number of visits with non-missing care model				
Over all participants Number of visits with non-missing care model Number of fast-track visits (%)				
Adherence				
	Overall	Control	Intervention	Intervention vs. control
	Count (proportion) / Median (IQR)			°RR (95% CI)
Per participant Number of intervals with good adherence				
Over all participants Number of intervals with good adherence Number of intervals with good adherence (%)				

^a Estimated by Poisson regression with robust errors

^b Estimated by Cox proportional hazards regression

^c Estimated by mixed-effects Poisson regression models with random effects for facility and participant and robust standard errors

*Models adjusted for any factors differing between arm with statistical significance at enrollment

Section 4. Missing data

While we will attempt to follow all participants at 12 months, we anticipate that EMR data and VL data may be incomplete for some participants might be a challenge due to participant loss to follow-up – either due to loss from care, or silent transfer to another facility. Due to the level of missingness we expect, we will not conduct any formal imputation.

Section 5. Safety monitoring

Adverse and severe adverse events, including social harms such as violence or breach of confidentiality, will be monitored as they arise, and unblinded results will be reviewed by the DSMB. The DSMB will make recommendations regarding any imbalances in safety outcomes.

SAE #	PTIDNO	Study arm	SAE description	Onset date	Duration (days / unresolved)	Onset since randomization (days)	Relatedness to study

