4.3 JUSTIFICATION FOR INTERVENTION

The intervention will be delivered by HCW during routine clinical visits; and works at improving clinic level effectiveness in care management. We anticipate at least 50 adolescents per site will be exposed to the intervention during the course of the study period. The intervention will be offered during regular clinic visits that are typically scheduled 1-6 monthly.

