2.1. Summary of primary and secondary outcomes

Table 1. Outcome definitions and assessment

Outcome	Indicator	Source	Timing
Primary outcome			
Retention in care	Missed visits: Not seen within 30 days of a scheduled visit.	EMR data (Visit Date, TCA)	All visits occurring during the 12-month period after the study enrollment visit*
Secondary outcomes			
Loss to follow-up	Not return to care within the 12 months study interval	EMR data (Visit Date, TCA)	All visits after the first study visit until event or end of follow-up at 12 months. Participants marked as 'transferred out' or 'died' will be censored.
Viral non-suppression	Having HIV viral load (VL) >1,000 copies/mL	NASCOP data, abstraction of paper records	All visits from enrollment to 12 months follow-up*
Receiving differentiated care	
 Long inter-visit interval Fast-track visit 	EMR data (TCA, Care Model)	All visits from enrollment to 12 months follow-up*
Adherence	Pill coverage estimated by days of dosing and inter-visit interval since last visit >80%	EMR data (Visit Date, next Visit Date, Duration)	All visits from enrollment to 12 months follow-up*

*time window up to 12 months + 30 days

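### Loss to follow-up has no absence threshold beyond the 30-day missed-visit rule, so the absence that counts as lost ranges from about 1 to 12 months with the date of the missed appointment

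*SAP*

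**What the plan says.** SAP 3.5.1 defines the event: "Loss to follow-up will be defined as a participant missed a visit and did not return to care within the 12-month study period". The loss to follow-up row of SAP Table 1 (section 2.1) gives the same rule more briefly: "Not return to care within the 12 months study interval". The missed visit it builds on is defined in SAP 3.4: "A missed visit will be defined as a participant not seen within 30 days of a scheduled visit during follow-up".

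The cut-off is given in two ways. SAP 3.5.1 has "window up to 12 months +30 days". Table 1 has "All visits after the first study visit until event or end of follow-up at 12 months", and its loss to follow-up row lacks the asterisk that gives the other rows the extra 30 days.

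The event is analysed twice: as a proportion by Poisson regression with robust errors, and as a time to event by survival curves and a Cox model, with death and transfer censored. The SAP does not say on which date the event falls. Protocol 9.4.2 names loss to follow-up and a Cox model but does not define the event. Neither document gives a separate minimum time out of care, a check for return after the window, or a sensitivity analysis with a fixed absence.

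**The concern.** The absence required is whatever time is left between the missed appointment and a common cut-off. Near month 12 the rule is almost the missed-visit rule; at month 1 it asks for about a year out of care. Two adolescents who behave alike can be scored oppositely, and the one with the longest gap can be scored as not lost.

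For the Cox model there is a second problem. A missed appointment becomes an event only if nobody sees the adolescent again before cut-off, so event status depends on the future. Late attenders become events mainly in the last months of follow-up, where there is least time left to return.

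Visit spacing also plays a part, because it sets how many appointments fall near the cut-off. Control sites have "usually 1-3 monthly visits" (Protocol 4.1), and the intervention is given at "regular clinic visits that are typically scheduled 1-6 monthly" (Protocol 4.3). DiSC is meant to change spacing, and scheduled intervals of 3 months or more are themselves a secondary outcome. The mixture of late attenders and true losses therefore need not be the same in both arms.

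**Working it through.** **The plan's own figure.** The only stated figure that rests on loss to follow-up is in SAP 2.2.1: 75% in care (not lost) at 12 months, and 12 facilities per arm to detect 89% with 150 per facility. Two-sided alpha 0.05 is assumed, and 0.10 is read as an ICC.

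- n per arm = (1.96 + 0.8416)² × (0.75×0.25 + 0.89×0.11) / 0.14² = 7.849 × 0.2854 / 0.0196 = 114.3
- design effect = 1 + 149 × 0.10 = 15.9
- facilities per arm = 114.3 × 15.9 / 150 = 12.1, against 12 stated

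That figure reproduces and is not in dispute. The rest concerns the definition.

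**Absence needed to be lost.** Take the first study visit as day 0 and 12 months as 365 days, so the cut-off is day 365 + 30 = 395. An appointment on day *a* counts as lost if the return is on day 396 or later, so the minimum lateness is 396 − *a* days. The missed-visit rule requires at least 31.

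| Appointment day | Minimum lateness to be lost |
|---|---|
| 365 | 31 days |
| 335 | 61 days |
| 270 | 126 days |
| 180 | 216 days |
| 90 | 306 days |
| 30 | 366 days |

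**Three records scored by the text.**

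- A: appointment day 364, return day 396, 32 days late. Needs 396 − 364 = 32. Lost.
- C: appointment day 180, return day 215, 35 days late. Needs 216. Not lost.
- B: appointment day 30, return day 394, 364 days late. Needs 366. Not lost.

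If the cut-off is day 365, as Table 1 can be read, the minimum becomes 366 − *a*. B is then lost, but a return on day 360 (330 days late, 336 needed) is still not lost. The 31-day floor moves to appointment day 335. The pattern stays.

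**Size, by illustration.** The documents give no lateness rates. Assume 20% permanent loss by 12 months, a proportion q = 3-5% of other appointments attended more than 30 days late, and delay beyond day 30 exponential with mean m = 30-90 days. Appointments fall every 30 or 90 days from the first visit; cut-off day 395. Simulation gives, for monthly visits:

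| q, m | Counted lost but return later (points) | Of these, over 90 days late | 90 days or less (points) |
|---|---|---|---|
| 3%, 30 | 2.9 | 35% | 2.9 × 0.65 = 1.9 |
| 3%, 60 | 5.0 | 71% | 5.0 × 0.29 = 1.5 |
| 5%, 60 | 8.1 | 69% | 8.1 × 0.31 = 2.5 |
| 5%, 90 | 11.4 | 83% | 11.4 × 0.17 = 1.9 |

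The last column is about 6-9% of counted losses (for example 1.9/21.7 = 9% in the first row, 1.9/28.6 = 7% in the last). For 3-monthly visits the first results column is 2.0, 2.7, 4.3 and 5.5 points, and the part at 90 days or less is about 1.3-2.0 points.

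The opposite error, a gap over 90 days scored as not lost, affects about 2.6-12% of participants with monthly visits and about 1-4% with 3-monthly visits.

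Hand check for q = 3%, m = 30. An absence of 90 days or less can be lost only if the appointment falls after day 305. With monthly visits those are days 330 and 360. The chance that a late return falls after day 395 but within 90 days is (e^(−35/30) − e^(−2)) + (e^(−5/30) − e^(−2)) = 0.176 + 0.711 = 0.887. Multiplied by 0.03, and by 0.8 still in care, this is 2.1 points, close to 1.9. With 3-monthly visits only day 360 counts: 0.711 × 0.03 × 0.8 = 1.7 points. Day 360 is an unfavourable alignment. If 3-monthly appointments are spread evenly over the calendar, the figure is (0.03/90) × [30(1 − e^(−2)) − 60e^(−2)] × 0.8 = (0.03/90) × 17.8 × 0.8 = 0.5 points.

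**Timing.** Under the same assumptions roughly 63-95% of late-attender events attach to appointments after day 270, against about 22-23% of permanent losses.

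**The case against.** Being out of care, without return, at the end of 12 months is a recognisable quantity. It matches the sizing assumption of 75% in care at the end of follow-up, and a returner such as record B is in care then. Missed appointments, including B's, still enter the primary repeated-measures analysis. This stands for the proportion, and is why that definition need not be discarded. It does not answer the Cox problem, nor the opposite scoring of A and C.

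The threshold of 90 days has no source in the documents, and an event that return does not undo is a different estimand. This also stands: the threshold is an analysis convention and needs a reason.

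Four stronger readings are tempting, and the documents do not support them.

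- That there is no minimum absence at all. The missed-visit rule sets a floor of more than 30 days.
- That 13-40% of counted losses are false. That share (2.9/21.7 to 11.4/28.6, monthly visits) includes everyone who ever returns, and in most of the settings the majority are over 90 days late, so a 90-day rule would also count them as lost.
- That the risk ratio is diluted. If DiSC halves permanent loss from 20% to 10% and late attenders add 5 points in each arm, the ratio moves from 0.50 to 15/25 = 0.60. But being more than 30 days late is the primary outcome DiSC is meant to improve. If late-attender events halve too, the ratio is 12.5/25 = 0.50.
- That proportional hazards fails. A Cox model leaves the baseline hazard free, so a late rise in both arms is no violation. Only a changing ratio between arms would be, and none is shown.

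**Conclusion.** The definition is inconsistent across participants, and this follows from the text and date arithmetic alone. One label covers absences from 31 to 366 days for appointments between day 365 and day 30, and event status in the Cox model depends on later returns.

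The size rests on assumed lateness rates and on how appointments align with the cut-off. About 1-2.5 points of counted loss are absences of 90 days or less (about half a point if 3-monthly appointments are evenly spread), and about 1-12% of participants have a gap over 90 days yet are scored not lost.

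The direction of any between-arm bias is not established. It changes with whether lateness is held equal per appointment or per unit of time. Loss to follow-up is a secondary outcome, and the primary missed-visit analysis does not use this definition.

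**What to change.** In SAP 3.5.1 and Table 1:

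1. Add a loss to follow-up event with one fixed absence for everyone, for example no visit for 90 days after a scheduled appointment. Date it at a fixed point, such as appointment + 90 days, and state that a later return does not undo it. Give the reason for the threshold.
2. Use this event for the Cox model and survival curves, and as a parallel or sensitivity analysis for the Poisson risk ratio.
3. Keep not returned by 12 months as the end-of-study proportion, named as such.
4. Give the same cut-off in Table 1 and 3.5.1.

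The 90 days can be observed in either of two ways: read EMR visit dates to 12 months + 90 days for appointments up to month 12, or keep the present window and use appointments up to day 395 − 90 = 305, about month 10.

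The visit and appointment dates are already listed as sources in Table 1, so the work is SAP wording and a re-derivation. The cost is about two more months of EMR visit dates (90 days rather than 30 past month 12), or about two months fewer appointments at risk. The second option weighs more on participants with visits up to 6 months apart, some of whom would keep only one appointment.
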